9.3 Demographic and Baseline Characteristics

The following summaries will be provided by treatment arm and total using ITT and PP Analysis Set:

- Demographic characteristics: sex, race, ethnicity, age, height and body weight at Screening, and body mass index at Screening.
- HAE history: history of laryngeal attack (yes, no), family history of HAE (yes, no), HAE type (C1-INH type 1, C1-INH type 2), prophylactic HAE therapy within 3 months before Screening (yes, no), number of HAE attacks before the start of prophylactic therapy, number of HAE attacks within 3 months before Screening, primary locations of HAE attacks in the last 3 months prior Screening.
- Medical history by system organ class (SOC) and preferred term (PT) – include medical history with an end date prior to informed consent date.
- Concomitant diseases by SOC and PT – include medical history with an end date after informed consent or flagged as ongoing.
- Stratification factors: age (≤ 17 year, > 17), baseline HAE attack rate observed during the Run-in Period (1 to < 3 attacks /month, and ≥ 3 attacks/month).

Technical Note: The baseline HAE attack rate as used for randomization will not be captured in eCRF and can be only obtained from the unblinded randomization file at the end of the study and/or blinded randomization files, if available.

Medical history and concomitant diseases will be coded by Medical Dictionary for Regulatory Activities (MedDRA). There will be periodic updates of the MedDRA version. The latest licensed version will be used, and version updates will be implemented upon availability.

By-subject listings for all available data using the Screened Analysis Set will be provided for each category mentioned above and further for:

- Reproductive system findings (childbearing potential, method of birth control, date and time of pregnancy test, specimen type, and pregnancy test result).

Those listings will further contain an ITT and PP flag.

9.4 Prior/Concomitant Medications

Reported medications will be coded using World Health Organization Drug Dictionary Enhanced (WHO-DDE, version used will be indicated in the corresponding TLF Shells). The summary of medications will show the number and percentage of subjects taking medication displayed for Anatomical Therapeutic Chemical (ATC) class level 4 and Preferred Term. If the level 4 ATC name is not available, then the level 3 ATC name will be used and if the level 3 ATC name is not available then the level 2 ATC name will be used.

The following classification of concomitant medication related to start date of study treatment period will be applied:

- Assign to 'Prior Only' if the concomitant medication start date and end date is prior to first study treatment start date; if the subject has not taken any study treatment; or the concomitant medication start date is missing and the concomitant medication end date is before the study treatment start date;
- Assign to 'Prior and Concomitant' if the concomitant medication start date is prior to first study treatment start date and the concomitant medication end date is on or after study treatment start date or ongoing treatment;
- Assign to 'Concomitant Only' if the concomitant medication start date is on or after the first study treatment start date.

If medication start and/or stop dates are partially or completely missing, medications will be assumed to be 'Concomitant Only', unless there is clear evidence (through comparison of partial dates) to suggest that the medication started prior to the date of the first study drug administration. If there is clear evidence to suggest that the medication started prior to the date of first study drug administration (the available parts of the date are prior to the corresponding parts of the date of first study drug administration), the medication will be assumed to be 'Prior and Concomitant', unless there is clear evidence to suggest that the medication stopped prior to the date of the first study drug administration (the available parts of the medication end date are prior to the corresponding parts of the date of first study drug administration of study). If this is the case, the medication will be considered 'Prior Only'.

In the summary of prior and concomitant medications, each subject will be counted once within each unique term. For example, if a subject takes Amoxycillin on 2 separate occasions, the subject is counted only once under the corresponding ATC class.

On-demand HAE medication will be summarized as separate block within the summaries of prior and concomitant medication (as a “virtual” ATC class “On-demand HAE Medication”). The on-demand HAE medication will also be reported in their original ATC class.

Technical Note: On-demand HAE medications prior to Run-in Period are collected in the CRF form ‘Concomitant and Prior Medications’ with Primary Indication as ‘Study Indication Acute HAE Treatment’. On-demand HAE medications on/after start of the Run-in Period are collected in a separate CRF form ‘On-demand Treatment’.

Summaries and by-subject listings will be given for Safety Analysis Set. Listings will include medication/therapy start and end date:time or ongoing status, dose, route, frequency, primary indication for the medication, AE term if applicable, medical history term if applicable and concomitant medication flag (Prior, Prior/Concomitant, Concomitant).

Separate summaries and listings are planned for COVID-19 vaccines, see [Section 7.1](#).

10 Efficacy Analyses

10.1 Analysis of Primary Endpoint

The primary endpoint is the time-normalized number of HAE attacks per month during the Treatment Period from Day 1 (first study drug administration) through Day 182 (inclusive).

Subjects will enter HAE symptoms into their eDiary, the start and end date and time, the interference of HAE symptom(s) with daily activities, and location(s) of the HAE symptom(s). Investigator-reported HAE attacks will be based upon review of subject diaries, relevant interval medical history, and physician judgment. The investigator may ask clarifying questions to assist in his/her assessment of whether or not an HAE attack occurred. If an attack occurred, then the investigator will record an attack in the eCRF form, the start/end date and time, the attack location(s), and the severity of the attack based on the most severe symptoms. For every visit, the investigator will report all HAE attacks that have occurred in the interim since the last visit the subject attended.

For all analyses considering HAE attacks, only the HAE attacks confirmed and reported by the investigator using the eCRF ‘HAE Attacks’ form will be used.

HAE attacks with a start date on or after the first day of the Run-in Period but prior to the date and time of the first study drug administration will be counted for the Run-in Period.

HAE attacks with a start date and time after the first study drug administration through Visit Day 182 (inclusive) or End of Study visit (whatever is first) will be counted for the Treatment Period and will be included in the analyses of efficacy.

The primary endpoint will be analyzed using the ITT and PP Analysis Set. The ITT Analysis Set will be used as the primary analysis and the PP Analysis Set will be used as the supplementary analysis (see [Section 10.1.3](#)).

The primary endpoint, time-normalized number of HAE attacks per month, is calculated per subject as:

$$[\text{the number of HAE attacks} / \text{length of subject treatment in days}] * 30.4375$$

where the length of subject treatment is calculated as:

$$[\text{the date of Study Visit Day 182 or the End of Study date [whatever is first]} - \text{the date of Study Visit Day 1 of the Treatment Period} + 1].$$

To transform the length of subject treatment which are calculated in days in years the number of days is divided by 365.25. Thus, time-normalized number of HAE attacks per year is calculated per subject as:

$$[\text{the number of HAE attacks} / \text{length of subject treatment in days}] * 365.25.$$

The time-normalized number of HAE attacks will not be calculated if the subject's observation time for the Treatment Period is less than 30 days, i.e. subject discontinued within 30 days after first study drug administration.

The randomization is stratified by the variables age (≤ 17 years, > 17 years) and, for adults, the subject's baseline attack rate (1 to < 3 attacks/month, and ≥ 3 attacks/month) during the Run-in period. Age and baseline attack rate are not regarded as confounder or effect modifier. The stratification by age is implemented to mitigate the risk that adolescent subjects could be randomized all to the same treatment, with worst case scenario that all adolescents are on placebo treatment. There is no significant physiological basis to suggest different efficacy or safety profiles in adults and adolescents and the distribution of attack locations in adolescent subjects typically mirrors that of adults [[MacGinnitie, 2014](#)].

It is expected that around 50% of subjects will have 1 to < 3 attacks/month and around 50% of subjects will have ≥ 3 attacks/month as baseline attack rate [[Banerji, 2018](#)]. Because of the stratified randomization these two subgroups of subjects will be equally distributed to the Active and to the Placebo arm. It is assumed that the treatment effect, i.e. the time-normalized number of HAE attacks observed under CSL312 treatment, is not impacted by the baseline attack rate. Nevertheless, the time-normalized number of HAE attacks will be compared for

the 6 months of the Active Arm and the 6 months of Placebo Arm using a Poisson Regression model including baseline attack rate as fixed effect in a sensitivity analysis, see [Section 10.1.2](#).

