10.3.2 Efficacy Analyses

10.3.2.1 Primary Estimand

The primary interest is to assess the treatment effect of CSL312 during treatment from Day 1 through Day 182 while subjects are allowed to treat HAE attacks with on-demand medications, administered according to [Section 5.2.1.1](#).

The primary estimand in line with the primary interest of the study follows the treatment policy strategy and is described as follows:

- Population: the target patient population defined by eligibility criteria and who were randomized (ITT).
- Variable: time-normalized number of HAE attacks during treatment from Day 1 through Day 182.
- Intercurrent events: The occurrence of an intercurrent event is irrelevant. All observed values will be used regardless of occurrence of any of the following intercurrent events:
 - administration of on-demand medication in addition to prophylactic treatment with CSL312.

- non-compliance to treatment.
- early discontinuation.
- Population-level summary: median time-normalized number of HAE attacks per month during treatment from Day 1 through Day 182 by treatment.

Subjects will be followed after failure to administer or to continue CSL312 treatment until their completion of the study, ie, Visit Day 182 or Early Termination Visit (whichever occurs first).

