4.5 Determination of the Sample Size

In total, 60 subjects are planned to be randomized.

Forty subjects with C1-INH HAE type 1 and type 2 completing the 6-month Treatment Period are needed to achieve a power of approximately 90% for a two-sided Wilcoxon Test (alpha of 5%). Subjects will be randomized to the Active Arm or the Placebo Arm with a ratio of 3:2. An attack rate per month of 0.3125 for CSL312-treated subjects and of 1.3 for subjects receiving placebo are assumed. The monthly attack rates of placebo and of CSL312 are assumed to be Poisson distributed.

The sample size calculation is performed with SAS 9.4 using proc power procedure with twosamplewilcoxon test=WMW which performs power analyses for the Wilcoxon-Test for two independent groups, i.e. the CSL312 and the Placebo treatment in Study CSL312_3001. The Wilcoxon Rank Sum test is testing from departure from the null hypothesis and is assessing if there is a location shift between the distributions of the HAE attack rates of the CSL312 and the Placebo treatment. SAS Proc Power procedure uses the O'Brien-Castelloe approach to compute approximate power. Alpha is set to 5% [O'Brien & Castelloe, 2006]. The assumed monthly attack rates of placebo and of CSL312 (i.e. 1.3 and 0.3125 attacks/month, respectively) are used as the two means of the two Poisson distributions. The randomization ratio of 3:2 was implemented by GROUPNS = (24 16) resulting in a total sample size of 40 which is the lowest one reaching 90% power.

It is targeted to randomize approximately 5 adolescents into the treatment period with a randomization ratio of 3:2 (active:placebo).

To allow for sufficient safety data, to increase the likelihood of adolescents entering the study and, to have at least 40 subjects reaching the end of the study, an additional 20 subjects are planned to be randomized.

In case it is not feasible to randomize the targeted number of adolescents, the targeted total sample size will be achieved by randomizing the needed number with adult subjects.

In addition, it is targeted to include 5 Japanese subjects into the total 60 subjects randomized.

Based on Method 1 and Method 2 in the [Basic principles on Global Clinical Trials] the sample size of the Japanese subjects are planned as below. The point estimate of the endpoint in each arm for Japanese population and other regions (for Method 2) are assumed as the same as that for the global population.

Method 1

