4.6.3 Independent Data Monitoring Committee

An independent data monitoring committee (IDMC) will be established to monitor the safety and efficacy data generated during the study. The IDMC will consist of an independent statistician and clinical specialists in the fields of HAE management, who also have experience in clinical trials. The IDMC will review accumulating data from the ongoing study. Based on these reviews, the IDMC will advise on the further conduct of the study. No success or futility thresholds will be set for the IDMC reviews; CSL will not stop the study unless a major safety issue has been identified. The composition, activities, and responsibilities of the IDMC will be described separately in the IDMC charter. A separate IDMC SAP and IDMC TFL Shells will be created.

5 Changes from the Protocol Planned Analyses

Estimand definition has been updated to reflect the potential impact of the ongoing coronavirus disease 2019 (COVID-19) pandemic, see [Section 7.1](#) and [Section 10.1.1](#).

Comparison of the distribution of responses to therapy between CSL312 and placebo at the end of the Treatment Period will use the ~~cci~~ at Visit Day 182 only. If subject's Study Visit Day 182 ~~cci~~ value is missing the subject will not be included in the ~~cci~~, see [Section 10.4](#).

Also, hypothesis H02 and hypothesis H04 have been defined more clearly by modifying the wording, see [Section 4.2](#).

There are no further changes to the analyses planned compared to the CSP. Any changes conducted after finalization of the SAP will be noted in the Clinical Study Report.

6 Study Analysis Sets

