10.1.1 Primary Estimand

The primary interest is to assess the treatment effect of CSL312 during treatment from Day 1 through Day 182 while subjects are allowed to treat HAE attacks with on-demand medications.

The primary estimand in line with the primary interest of the study follows the treatment policy strategy and is described as follows:

- Treatment Condition: monthly treatment of CSL312 or placebo
- Population: the target patient population defined by eligibility criteria and who were randomized (ITT).
- Variable: time-normalized number of HAE attacks per month during treatment from Day 1 through Day 182.

Intercurrent events: The occurrence of an intercurrent event is irrelevant. All observed values will be used regardless of occurrence of any of the following intercurrent events:

- administration of on-demand medication in addition to prophylactic treatment with CSL312,
- Prohibited concomitant medications due or not due to COVID-19 or COVID-19 vaccination,
- non-compliance to treatment due or not due to COVID-19 or COVID-19 vaccination,
- early study discontinuation due or not due to COVID-19.

- Population-level summary: median time-normalized number of HAE attacks per month during treatment from Day 1 through Day 182 by treatment.

If a subject discontinued the study early after being continuously the first 30 days in the treatment period, the observation is terminated by the Early Termination Visit. It is assumed that the attack rate for subjects, who discontinued the study after the 30th study day and before the end of the 6th month, is comparable to the attack rate from subjects who have the entire 6 months treatment period observed. This assumption is based on CSL312_2001 data which showed that the CSL312 treatment effect was maintained over time. Therefore, the primary endpoint will be considered measurable and not missing, ie, the time-normalized number of HAE attacks will be calculated based on the HAE attacks reported until the Early Termination Visit.

In case a subject discontinues study treatment due or not due to COVID-19 but continues participation in the study for more than 30 days beyond the last study drug administration,

the HAE attacks until the last study drug administration plus 30 days will be included in the HAE attack analysis and length of subject treatment in days will be derived as:

[date of last study drug administration – the date of Study Visit Day 1 of the Treatment Period +31].

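### The SAP's 30-day minimum removes the earliest study leavers from the primary ITT test, contradicting the treatment-policy estimand and the protocol formula, and SAP Section 5 does not declare it

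*SAP*

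**What the plan says.** **The rule.** SAP Section 10.1 gives no attack rate to a subject whose "observation time for the Treatment Period is less than 30 days". SAP Sections 8.1 and 10.1.1 say the same in other terms: a subject who leaves the study within 30 days of first dose has a missing endpoint, and this is the only source of missing data.

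**The estimand.** SAP Section 10.1.1 takes the randomized population, follows treatment policy, and says: "All observed values will be used regardless of occurrence of any of the following intercurrent events". Early study discontinuation is on the list that follows. Protocol Section 10.3.2.1 has the same construction ("Intercurrent events: The occurrence of an intercurrent event is irrelevant") and also lists early discontinuation.

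**The formula.** Protocol Section 10.3.2.3 divides attacks by days from Day 1 to the Day 182 visit or study discontinuation, whichever comes first, and multiplies by 30.4375. It sets no minimum duration.

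**The change list.** SAP Section 5 names three items: a COVID-19 update to the estimand, use of Day 182 only for the response-to-therapy assessment, and clearer wording of H02 and H04. It then states: "There are no further changes to the analyses planned compared to the CSP".

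**The safeguards.** SAP Section 10.1.2 expects very few subjects with a missing endpoint. It plans to impute all combinations of 0 to 6 attacks/month in the two arms and rerun the Wilcoxon test. It also plans a Poisson regression with log treatment length as offset, indexed over the ITT set.

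**The concern.** A subject who leaves on day 20 has an observed attack count and an observed duration. Under the protocol formula that subject has a rate; under the SAP the subject is missing. The exclusion depends on something that happens after randomization and may be related to treatment or to disease activity, which is the selection that an ITT treatment-policy analysis is meant to prevent.

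Two results are affected. The primary Wilcoxon test (H01) is run on the per-subject rate, so these subjects drop out of it. H02 compares arm means of the same rate (SAP Sections 4.2 and 10.3.2.4), so they drop out there too, and no missing-data analysis is specified for H02. A reader who relies on Section 5 would not learn that the rule departs from the protocol.

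**Working it through.** **1. The plan's own figure.** Inputs from SAP Section 4.5: "An attack rate per month of 0.3125 for CSL312-treated subjects and of 1.3 for subjects receiving placebo are assumed", Poisson distributed, two-sided alpha 5%, and "GROUPNS = (24 16) resulting in a total sample size of 40 which is the lowest one reaching 90% power". Applying the O'Brien-Castelloe method that the SAP names to the two Poisson distributions gives power 0.907 at 24 + 16, against 0.872 at 21 + 14, the next smaller exact 3:2 split. A simulation of 20,000 trials gives 0.921 at 24 + 16. The stated 90% is reproduced, and nothing in this point changes it.

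**2. The texts side by side, for a subject who leaves the study on day 20.**

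| Source | Treatment of this subject |
|---|---|
| Protocol 10.3.2.1 and 10.3.2.3 | Rate = attacks / days x 30.4375; included |
| SAP 10.1.1, estimand | Randomized; early study discontinuation irrelevant; observed data used |
| SAP 10.1, 8.1 and missing-data text in 10.1.1 | No rate; missing; not in the Wilcoxon test |

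The last row cannot be reconciled with the first two.

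**3. Who is not affected.** For a subject who stops treatment but remains in the study more than 30 days after the last dose, SAP Section 10.1.1 sets the length at last dose date - Day 1 + 31. After a single dose on Day 1 this is 0 + 31 = 31 days, so the subject is counted.

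**4. Size for H02, under assumed numbers of leavers.** "In total, 60 subjects are planned to be randomized", which at 3:2 is 36 active and 24 placebo. Take k active leavers with observed rate r and all other subjects at the planning rates:

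active mean = [(36 - k) x 0.3125 + k x r] / 36; reduction = 1 - active mean / 1.3

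| Leavers kept (k, r) | Active mean | Reduction |
|---|---|---|
| Leavers dropped (SAP rule) | 0.3125 | 76.0% |
| 1, r = 1.3 | (10.9375 + 1.3)/36 = 0.340 | 73.9% |
| 2, r = 1.3 | (10.625 + 2.6)/36 = 0.367 | 71.7% |
| 1, r = 3 | (10.9375 + 3)/36 = 0.387 | 70.2% |
| 2, r = 3 | (10.625 + 6)/36 = 0.462 | 64.5% |

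The direction is not fixed. One placebo leaver at 3/month, if kept, gives a placebo mean of (23 x 1.3 + 3)/24 = 1.371 and a reduction of 1 - 0.3125/1.371 = 77.2%, so dropping that subject would understate the effect.

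**5. Size for H01, by simulation at 36 + 24 over 182 days.** Under the plan's Poisson rates, power is about 100% whether leavers are kept or dropped. With assumed between-subject variation (gamma, shape 1) and 3 active leavers on days 5 to 29 at 3/month, power is 93.8% kept and 96.9% dropped. The typical active median does not move.

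A deliberately adverse null case assumes equal arms with the same variation, where the active subjects with the highest rates leave at day 20:

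| Active leavers | Type I error, dropped | Type I error, kept |
|---|---|---|
| 1 | 5.6% | 5.0% |
| 2 | 7.0% | 5.2% |
| 3 | 8.9% | 5.5% |
| 4 | 11.4% | 5.6% |

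**6. Reach of the grid.** It is specified for the Wilcoxon test only, and it replaces the rates that were observed. An observed rate can also lie outside it: 2 attacks in 9 days is 2/9 x 30.4375 = 6.8/month.

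**The case against.** The rule is pre-specified, stated in several sections, and has a rationale. One attack in 10 days becomes 3.0/month, against 0.17/month for one attack in 182 days, so very short observation gives a noisy rate. The protocol leaves the full description of methods to the SAP. Few subjects are expected, and the grid tests H01 over a range that contains both rates used above. The Poisson model works on counts with an offset and needs no individual rate, so early leavers could contribute their observed data to a mean-based check close to H02. Section 5 does point to Section 10.1.1, where 30-day text appears.

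Most of this stands as a limit on consequence. It does not remove the contradiction: the estimand still claims all observed values, Section 5 labels the Section 10.1.1 change as COVID-19 related only although the rule applies whatever the cause, and the SAP does not say whether the Poisson model includes subjects under 30 days.

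Three stronger readings are tempting and not supported:

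- A reader might infer that anyone who stops after a reaction to the first dose disappears. Only leaving the study within 30 days triggers the rule, and both documents encourage subjects who stop treatment to remain to Day 182.
- A reader might take 64.5% as the expected result. It assumes active leavers only, at more than twice the plan's placebo rate. At 1.3 the figure is 71.7%.
- A reader might substitute the Run-in rate for these subjects as a conservative value. It is not an observed treatment-period value, and it is not conservative in the placebo arm: entry requires at least 2 Run-in attacks, and SAP Section 10.1 expects about half of subjects at 3 or more per month, while placebo is planned at 1.3. One placebo leaver set to 3 moves the reduction from 76.0% to 77.2%, in favour of CSL312.

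**Conclusion.** The point holds. The 30-day minimum is a post-randomization exclusion from the primary ITT test. It contradicts the estimand in both documents and the protocol's endpoint formula, and SAP Section 5 does not declare it. The grid covers H01; nothing equivalent is specified for H02.

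The size cannot be known from the documents, which give no early-leaver count. For 1 or 2 active leavers at 1.3 to 3 attacks/month, the H02 reduction would lie between 73.9% and 64.5% instead of 76.0%; placebo leavers could move it the other way. These figures rest on the planning rates and assumed leavers. The documents do not support a claim that the primary conclusion is likely to change: under the plan's Poisson rates power is about 100% either way, and the inflated type I error needs selective exit of the worst active subjects. It should be corrected because the defect is in the definition and the remedy is cheap.

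**What to change.** - In the primary Wilcoxon test and the H02 means, calculate the rate for every randomized subject with any treatment-period observation by the protocol formula: observed attacks / observed days x 30.4375.
- Make the 30-day exclusion a sensitivity analysis.
- Keep the 0 to 6 grid for randomized subjects with no treatment-period observation, and extend it to H02.
- State that the Poisson offset model includes early leavers with their observed counts and days.
- If the 30-day rule is kept as primary, list it in SAP Section 5 as a change from the protocol and amend the estimand so that it no longer claims all observed values.
- Do not use the Run-in rate as the primary value.

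The cost is SAP wording and a small amount of programming; sample size and power do not change. The downside is a noisy rate for a few subjects. This has limited influence on a rank test but can affect the H02 means, which is why the 30-day exclusion remains useful as a sensitivity analysis.
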